4.12.3 Statistical Analysis of Pharmacokinetic Data

Drug concentration-time data will be listed for each subject and summarized by descriptive statistics at each nominal collection time. Pharmacokinetic parameters will be listed for each subject and summarized by descriptive statistics. Specimens will also be analyzed for the presence of anti-raxibacumab antibodies. Those results will be descriptively and/or graphically summarized as appropriate to the data.

4.12.4 Safety Analyses

All safety assessments, including AEs, clinical laboratory evaluations, and vital signs will be listed and where appropriate summarized with descriptive statistics.

4.12.4.1 *Summary of Exposure*

Study treatment administration will be listed and summarized for AVA with the number (%) of subjects receiving dose on Day 1, Day 15 and Day 29.

4.12.4.2 *Adverse Events*

An AE is any untoward medical occurrence in a patient or clinical investigation subject, temporally associated with the use of a medicinal product, whether or not considered related to the medicinal product. An AE can therefore be any unfavorable and unintended sign (including an abnormal laboratory finding), symptom, or disease (new or exacerbated) temporally associated with the use of a medicinal product. The period of observation for AE reporting will begin from the start of study treatment until the follow-up contact.

All AEs will be coded to body system and preferred term using the Medical Dictionary for Regulatory Activities (MedDRA) dictionary, 17.1.

A treatment-emergent adverse event (TEAE) is defined as any AE that began or worsened following the start of dosing. A treatment-related AE is defined as any TEAE that is assessed by the Investigator as having a reasonable possibility that the AE may have been caused by the study treatment or those for which the relationship is missing.

The total number and percentage of subjects with TEAEs will be presented by system organ class and preferred term for each study treatment and for all subjects overall. Treatment-emergent adverse events will also be presented by maximum grade according to the Division of Microbiology and Infectious Diseases (DMID) toxicity tables (Appendix 6 of the study protocol). For AEs not included in the appendix above, the following guidelines will be used:

Mild: An event causing no limitation of usual activities.

Moderate: An event causing some limitation of usual activities.

Severe: An event causing inability to carry out usual activities.

Life threatening: An event that is potentially life threatening or disabling.

Treatment-emergent adverse events will be tabulated presenting the system organ class alphabetically and within each system the preferred term will be presented in decreasing order of the total number of subjects who experienced each TEAE. Treatment-related adverse events will be similarly presented.

To count the number of subjects who experience each TEAE or treatment-related AE, a subject experiencing the same AE multiple times will only be counted once for that preferred term. Similarly, if a subject experiences multiple AEs within the same system organ class, that subject will be counted only once for that system. If changes in the DMID grade/severity of an AE are recorded in the eCRF, only the maximum grade/most severe incidence of the AE will be counted. For the summary of treatment-related AEs, if a subject experiences multiple occurrences of a TEAE then the subject will be counted as having a treatment-related TEAE if any of the events were treatment-related within each system organ class or preferred term, regardless of whether the subject also had an event of the same system organ class or preferred term which was not noted as treatment-related.

Pretreatment AEs are defined as AEs occurring prior to dosing. These events will be presented in the listings only and are not included in the tabular summary of AEs. See Appendix A for handling of partial dates for AEs. In the rare case where it is not possible to assess treatment emergence, the AE will be classified as treatment emergent.

Listings of all AEs, AEs leading to withdrawal from study or permanent discontinuation of study treatment, serious adverse events (SAE), and deaths, if any, will be provided. If deemed relevant (depending on the number of such events observed), summaries of SAEs, AEs leading to discontinuation of study drug, and deaths (with primary cause) will be provided using the same procedure as for TEAE.

4.12.4.3 *Pregnancies (as applicable)*

A listing of all female subjects of childbearing potential who become pregnant during the study will be provided.

4.12.4.4 *Clinical Laboratory Evaluations*

All laboratory data will be converted into Système International (SI) units for the analysis.

Protocol-specified clinical laboratory findings (serum chemistry and hematology) will be summarized using descriptive statistics. The statistics will be presented for baseline, each scheduled assessment during the study, and change from baseline to each scheduled assessment.

Based upon laboratory normal ranges, these laboratory test results will be categorized as low (below the lower limit), normal (within normal range), and high (above upper limit). For each treatment, shift tables comparing the distributions of these 3 categories at baseline versus Week 4 (and Week 8) evaluation will be presented for serum chemistry and hematology.

For non-continuous urinalysis variables, data will be summarized by counts and percentages based on the result of test.

Listings of all clinical laboratory data for each subject will be provided with values outside the normal ranges indicated. Scheduled post-baseline laboratory values will be tabulated. A listing of all abnormal laboratory findings will be provided.

The following liver chemistry stopping criteria will be applied to absolute ALT. Occurrences of these abnormalities will be listed separately:

1. ALT $\geq 3 \times$ upper limit of normal (ULN)
2. ALT $\geq 3 \times$ ULN and bilirubin $\geq 2 \times$ ULN ($> 35\%$ direct bilirubin)
3. ALT $\geq 3 \times$ ULN and international normalized ratio (INR) > 1.5

Criteria (2) and (3) will also be reported as SAE.

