4.2. Treatment Arms and Duration

Subjects will be randomized into one of the following two treatment groups:

- **Treatment Group 1-** subjects will be administered subcutaneous (SC) 0.5 mL AVA doses on Days 1, 15, and 29 (0, 2, and 4 weeks).
- **Treatment Group 2-** subjects will be administered SC 0.5 mL AVA doses on Days 1, 15, and 29 (0, 2, and 4 weeks), with the first AVA dose administered immediately after completion of a single IV infusion 40 mg/kg raxibacumab dose. Subjects will be premedicated with 25-50 mg of diphenhydramine up to 1 hour prior to the raxibacumab infusion to reduce the risk of infusion reactions.

Subjects will begin the study with a screening visit up to 35 days before the start of study treatment on Day 1. Results of the screening test for the anti-PA Ab levels must be available prior to randomization on Day -1. Study visits will occur at Days -1, 1, 15, 29, 57, and 183 (Week 26). The total study duration for each subject may be approximately 28 to 31 weeks.

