4.6. Benefit:Risk Assessment

Summaries of findings from both clinical and non-clinical studies conducted with raxibacumab (GSK3068483) can be found in the IB. Summaries of findings from both clinical and non-clinical studies conducted with AVA can be found in the prescribing information [[Anthrax Vaccine Adsorbed Package Insert, 2012](#)]. The following section outlines the risk assessment and mitigation strategy for this protocol

Clinical parameters will be monitored throughout the study in order to assess the safety and tolerability of AVA when administered alone or concomitantly with raxibacumab. The study design in place will allow in-stream blinded review of the aggregated safety and tolerability data during the study. Refer to protocol Section 7.1 for the timing of all clinical assessments.

Risk Assessment

Potential Risk of Clinical Significance	Summary of Data/Rationale for Risk	Mitigation Strategy
Study Drug		
Infusion Site Reactions (ISRs)	Infusion-related reactions were reported during administration of raxibacumab in clinical trials in healthy volunteers including reports of rash, urticaria, and pruritus.	Subjects will be premedicated with 25-50 mg of diphenhydramine up to 1 hour prior to the raxibacumab infusion, as recommended in the product label. Close monitoring of clinical parameters and adverse events will be conducted to assess effects of infusion site reactions.
Other		
Injection-site reactions	The most common ($\geq 10\%$) local (injection-site) adverse reactions observed in clinical studies with AVA were tenderness, pain, erythema, edema, and arm motion limitation.	Close monitoring of clinical parameters and adverse events will be conducted to assess effects of injection-site reactions.

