2.6 Study Schedule

The study will be comprised of a screening period (Days -36 to -15) and a treatment period (Days -1 to 183 ± 4). The complete schedule of visits and all procedures is presented in Table 2. 1, Table 2. 2, and Table 2. 3

Table 2.1 Screening assessments for subjects administered AVA or co-administered raxibacumab and AVA

Screening Assessments	Days -36 to -15 ^a	Notes
Informed consent process	X	
Demographic information	X	
Inclusion/Exclusion criteria	X	
Medical history (includes substance usage and Family history of premature CV disease)	X	
Physical exam including height and weight	X	
Alcohol and Drug Screening	X	
Urinalysis	X	
Vital signs	X	
Hematology and clinical chemistry	X	Refer to Table 4 in CSP [1] for specific laboratory tests.
HIV, Hep B and Hep C screen	X	
Review concomitant medications	X	
Serum or urine pregnancy test	X	
AE/SAE assessment	X	Will capture SAEs reported between Screening visit and Day -1.
Toxin Neutralizing Ab (TNA)	X	
Anti-PA Ab	X	

a. The screening window closes at Day -15 to allow all analyses to be completed to confirm subject eligibility.

Table 2.2 Treatment Group 1: Time and Events for subjects administered AVA

Protocol Activity	Study Visit						Notes
Assessments	Day -1 ^a	Day 1	Day 15 (± 2 days)	Day 29 (± 2 days)	Day 57 (± 2 days)	Day 183 (± 4 days)	
Inpatient visit		↔ X →					
Outpatient visit				↔ X →			
Urinalysis					X		
Admit to unit	X						
Randomization	X						
Discharge from unit		X					The subject will be discharged from the unit after all assessments are completed.
Vital signs	X	X		X	X	X	
Hematology and clinical chemistry	X			X	X		Refer to Table 4 in CSP [1] for specific laboratory tests. On Day 29 the specimen will be collected
Review concomitant medications	X		X	X	X	X	
Serum or urine pregnancy test	X		X	X	X	X	
AVA administration		X	X	X			Each sequential AVA injection will be administered in a different injection site (e.g. alternating arms).
AE/SAE assessment	X	X	X	X	X	X	
Toxin Neutralizing Ab (TNA)		X		X	X	X	On Days 1 and 29 the specimen will be collected prior to AVA injection.
Anti-PA Ab		X		X	X	X	On Days 1 and 29 the specimen will be collected prior to AVA injection.

a. Day -1 is the calendar day preceding Day 1; the designation "Day 0" is not used in this study.

Table 2.3 Treatment Group 2: Time and Events Table for subjects co-administered raxibacumab and AVA

Protocol Activity Assessments	Study Visit								Notes	
	Day -1 ^a		Day 1							

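### The once-per-term TEAE count over three AVA doses and 26 weeks attenuates a difference confined to the dose given with raxibacumab, and no by-dose table is planned to show it

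*SAP*

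**What the plan says.** The safety objective (SAP 2.1.2) is to describe the safety of AVA given with raxibacumab against AVA alone. AVA is given on Days 1, 15 and 29 in both arms. In Group 2 raxibacumab is given once, "with the first AVA dose administered immediately after completion of a single IV infusion 40 mg/kg raxibacumab dose" (Protocol 4.2).

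SAP 4.12.4.2 sets one observation window: "The period of observation for AE reporting will begin from the start of study treatment until the follow-up contact". The last scheduled visit is Day 183 (SAP 2.6). The table layout is: "The total number and percentage of subjects with TEAEs will be presented by system organ class and preferred term for each study treatment". Within it, "a subject experiencing the same AE multiple times will only be counted once for that preferred term", and where the grade of an event changes, "only the maximum grade/most severe incidence of the AE will be counted". SAP Appendix A classifies events only against the start of study medication. Protocol 9.4.2.3 plans the same kind of summary.

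Neither document plans a TEAE table by AVA dose or onset interval, or a separate injection-site analysis. The interim outputs in SAP 4.9 name none either. Yet Protocol 4.6 lists injection-site reactions as one of two named risks and promises: "Close monitoring of clinical parameters and adverse events will be conducted to assess effects of injection-site reactions". The by-dose counts needed for denominators are already planned, since exposure is "summarized for AVA with the number (%) of subjects receiving dose on Day 1, Day 15 and Day 29" (SAP 4.12.4.1).

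**The concern.** Dose 1 is the only AVA injection at which the two arms receive different products. Protocol 4.4 places it where raxibacumab levels are highest, as the worst case for an interaction (said there of immunogenicity). At doses 2 and 3 both arms receive the same injection.

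Under the once-only rule, a subject who reacts after any of the three doses contributes one count, whichever dose it was. A Group 2 subject who reacts at dose 1 because of raxibacumab, and who would have reacted at dose 2 or 3 anyway, adds nothing to the difference between arms. The maximum-grade summary works the same way: a higher grade after dose 3 hides the grade after dose 1.

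At stake is the summary that readers will use for the safety objective. A real change in reactions at the co-administered dose would look smaller than it is. A difference that did appear could not be attributed to the first dose or to continuing exposure.

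**Working it through.** **The plan's own figure.** The documents state no sample size, test or margin for adverse events. Their only such figure is 80% power for the immunogenicity test with 534 analyzable subjects. It reproduces at 0.7999 from the three stated boundaries (1.0274, 0.4437, -1.645 at 30, 100 and 534 subjects). It serves here only to supply 267 per arm.

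**Inputs.** Three AVA doses, one of them with raxibacumab (Protocol 4.2). Local reaction frequency: only 10% or more, not stated per dose (Protocol 4.6). The per-dose rates below are therefore assumptions.

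**Model.** Let p be the per-dose reaction rate with AVA alone and q the dose-1 rate in Group 2, with rate p in Group 2 at doses 2 and 3. With independent doses:

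- ever counted, Group 1: 1 - (1-p)^3
- ever counted, Group 2: 1 - (1-q)(1-p)^2
- difference: (q-p)(1-p)^2

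The pooled table keeps the fraction (1-p)^2 of the dose-1 risk difference.

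**Result for a 15-point excess at dose 1 only.** The Wald z at 267 per arm is only a yardstick of sensitivity, because no AE test is planned.

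| p | q | Group 1 ever | Group 2 ever | Difference kept | Fraction | z, dose 1 | z, pooled |
|---|---|---|---|---|---|---|---|
| 10% | 25% | 27.10% | 39.25% | 12.15 points | 81% | 4.7 | 3.0 |
| 30% | 45% | 65.70% | 73.05% | 7.35 points | 49% | 3.6 | 1.85 |
| 50% | 65% | 87.50% | 91.25% | 3.75 points | 25% | 3.5 | 1.4 |

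Example, p = 30%: 1 - 0.7^3 = 0.657; 1 - 0.55 × 0.49 = 0.7305; difference 0.15 × 0.49 = 0.0735.

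**Within-subject correlation.** With an equicorrelated latent-normal model and correlation 0.3 to 0.95, the fraction kept is 64-73% for 10% against 20%, 48-62% for 30% against 45%, and 31-57% for 50% against 65%. Correlation makes the loss worse at the low rate and milder at the high rate. The dose-1 difference shrank in every scenario tried.

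**Effect at all three doses.** With 15 points added at each dose, the pooled table shows 27.1% against 1 - 0.75^3 = 57.8% at p = 10%, and 65.7% against 1 - 0.55^3 = 83.4% at p = 30%. At p = 50% it shows 87.5% against 1 - 0.35^3 = 95.7%; power at two-sided 5% is 94% for one dose and 93% pooled. Such an effect is not lost.

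**The two patterns cannot be told apart.** At p = 30%, the pooled 73.05% in Group 2 arises from 45% at dose 1 and 30% afterwards. It arises equally from a constant q with (1-q)^3 = 0.2695, that is 1-q = 0.646 and q = 35.4% at every dose.

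**The case against.** The case against is substantial.

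- **Safety is descriptive, and once-per-term counting is conventional.** This stands. No planned decision depends on the table, and the AE listings keep every event. It limits the severity. But Protocol 9.4.2.3 says TEAE incidence will be compared between groups, and listings do not give by-arm rates with per-dose denominators. A split chosen after the data are seen also carries less weight than one fixed now.
- **Raxibacumab persists.** Protocol 4.4 expects protection for up to 28 days, so the antibody is present at the Day 15 dose and perhaps at Day 29. This stands: the attenuation concerns only an effect confined to dose 1. It does not answer the second half of the point, that the pooled table cannot distinguish the two patterns.
- **A dose-1 comparison has biases of its own.** This stands and must be stated with the table. Only Group 2 receives diphenhydramine before dose 1. Group 2 also has several Day 1 AE assessment columns (Protocol Table 3) against one in Group 1 (Table 2), in an open-label trial.

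A reader might infer that the pooled rates run into a ceiling in both arms. The documents do not support that. At 10% per dose they are 27% against 39%. A near-ceiling needs about 50% or more per dose and weak within-subject correlation; at 50% with a random-intercept logit of SD 2, the rates are 72.7% against 78.3%. No document puts any reaction that high.

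A reader might also infer that early stopping of AVA in Group 2 would flatter the combination. That is not supported either. A subject who stops because of a reaction is already counted, and doses received are summarized by day. An assumed 5% stopping after dose 1 with average risk moves the Group 2 rate by only 0.05 × (0.3925 - 0.25) = 0.7 points (p = 10%) to 0.05 × (0.7305 - 0.45) = 1.4 points (p = 30%).

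**Conclusion.** The point holds as attenuation and loss of attribution. If the effect is confined to the co-administered dose and doses are independent, the planned table keeps about 81% of the dose-1 risk difference at 10% per dose, 49% at 30% and 25% at 50%. All three rates are assumptions, and correlation shifts the fractions as shown. The fractions do not depend on sample size; the z-values assume 267 per arm, which is the analyzable target and not the Safety population, and would be smaller if the trial stopped at an interim. The loss is in the summary tables, not in the data, and the primary immunogenicity conclusion is unaffected. This is a cheap improvement to the SAP rather than a flaw that undermines the trial.

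**What to change.** Keep the planned TEAE tables. Add to SAP 4.12.4.2 one descriptive table with these rules:

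- **Onset intervals:** dose 1 to before dose 2; dose 2 to before dose 3; dose 3 to Day 57; after Day 57.
- **Counting:** each subject once per preferred term within each interval, plus a grouped row for any injection-site reaction from a term list fixed in advance.
- **Denominator:** subjects who received the AVA dose that opens the interval. No dose opens the interval after Day 57, so keep the dose-3 denominator there.
- **Comparison:** by-arm difference with 95% CI, by a named method, for the dose-1 interval only.
- **Footnote:** the dose-1 contrast reflects raxibacumab together with diphenhydramine premedication, and Group 2 has more Day 1 AE assessments than Group 1 in an open-label trial.

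The cost is one more descriptive output and a date rule that Appendix A lacks. An onset on a dosing day could go to the interval opened by that dose, in line with Appendix A's on-or-after convention. A partial onset date that fits more than one interval could be shown in a separate row. No new data are needed: AEs are assessed at every visit, dose dates and times are recorded (Protocol 6.6), and per-dose counts are already planned.

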4.12.4.5 Vital Signs

Vital signs (temperature, respiratory rate, pulse rate, and systolic and diastolic blood pressure) will be summarized by treatment using descriptive statistics for baseline, each scheduled assessment, and change from baseline to each scheduled assessment. Listings of all vital signs data will be provided.

4.13 Changes from Analyses Planned in Protocol

Electrocardiogram intervals will be listed for only those subjects that had the procedure performed after experiencing an AE.

5.0 SUBJECT DATA LISTINGS

Subject listings of all the data collected in the study database, including data recorded in the eCRFs and any external data transfers (such as clinical laboratory results), will be presented.

APPENDIX A. PARTIAL DATE CONVENTIONS

Imputed dates will NOT be presented in the listings.

ALGORITHM FOR TREATMENT EMERGENCE OF ADVERSE EVENTS:

START DATE	STOP DATE	ACTION
Known	Known	If start date < study med start date, then not TEAE If start date >= study med start date, then TEAE
	Partial	If start date < study med start date, then not TEAE If start date >= study med start date, then TEAE
	Missing	If start date < study med start date, then not TEAE If start date >= study med start date, then TEAE
Partial, but known components show that it cannot be on or after study med start date	Known	Not TEAE
	Partial	Not TEAE
	Missing	Not TEAE
Partial, could be on or after study med start date	Known	If stop date < study med start date, then not TEAE If stop date >= study med start date, then TEAE
	Partial	Impute stop date as latest possible date (i.e. last day of month if day unknown or 31st December if day and month are unknown), then: If stop date < study med start date, then not TEAE If stop date >= study med start date, then TEAE
	Missing	Assumed TEAE
Missing	Known	If stop date < study med start date, then not TEAE If stop date >= study med start date, then TEAE

START DATE	STOP DATE	ACTION
	Partial	
Impute stop date as latest possible date (i.e. last day of month if day unknown or 31st December if day and month are unknown), then:
 
If stop date < study med start date, then not TEAE
 
If stop date >= study med start date, then TEAE

	Missing	Assumed TEAE

ALGORITHM FOR PRIOR / CONCOMITANT MEDICATIONS:

START DATE	STOP DATE	ACTION
Known	Known	
If stop date < study med start date, assign as prior
 
If stop date >= study med start date and start date <= end of treatment, assign as concomitant
 
If stop date >= study med start date and start date > end of treatment, assign as post study

	Partial	
Impute stop date as latest possible date (i.e. last day of month if day unknown or 31st December if day and month are unknown), then:
 
If stop date < study med start date, assign as prior
 
If stop date >= study med start date and start date <= end of treatment, assign as concomitant
 
If stop date >= study med start date and start date > end of treatment, assign as post treatment

	Missing	
If stop date is missing could never be assumed a prior medication
 
If start date <= end of treatment, assign as concomitant
 
If start date > end of treatment, assign as post treatment

Partial	Known	
Impute start date as earliest possible date (i.e. first day of month if day unknown or 1st January if day and month are unknown), then:
 
If stop date < study med start date, assign as prior
 
If stop date >= study med start date and start date <= end of treatment, assign as concomitant
 
If stop date >= study med start date and start date > end of treatment, assign as post treatment

START DATE	STOP DATE	ACTION
	Partial	
Impute start date as earliest possible date (i.e. first day of month if day unknown or 1st January if day and month are unknown) and impute stop date as latest possible date (i.e. last day of month if day unknown or 31st December if day and month are unknown), then:
 
If stop date < study med start date, assign as prior
 
If stop date >= study med start date and start date <= end of treatment, assign as concomitant
 
If stop date >= study med start date and start date > end of treatment, assign as post treatment

	Missing	
Impute start date as earliest possible date (i.e. first day of month if day unknown or 1st January if day and month are unknown), then:
 
If stop date is missing could never be assumed a prior medication
 
If start date <= end of treatment, assign as concomitant
 
If start date > end of treatment, assign as post treatment

Missing	Known	
If stop date < study med start date, assign as prior
 
If stop date >= study med start date, assign as concomitant
 
Cannot be assigned as 'post treatment'

	Partial	
Impute stop date as latest possible date (i.e. last day of month if day unknown or 31st December if day and month are unknown), then:
 
If stop date < study med start date, assign as prior
 
If stop date >= study med start date, assign as concomitant
 
Cannot be assigned as 'post treatment'

	Missing	Assign as concomitant

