7.2. Screening and Critical Baseline Assessments

After written informed consent is provided, the following data will be collected at the screening visit for all subjects:

- Demographic parameters: year of birth, gender, race, and ethnicity.
- Medical/medication/family history will be assessed as related to the inclusion/exclusion criteria listed in Section 5.
- Physical assessment data including vital signs (temperature, heart rate, systolic and diastolic blood pressure, respiratory rate), height and weight.
- Laboratory assessments (hematology, clinical chemistry)
- Urinalysis
- Alcohol, Drug, HIV, Hepatitis B and Hepatitis C screenings
- A serum or urine pregnancy test on women of childbearing potential
- Blood specimen for anti-PA Ab levels and TNA titers.
- Record of concomitant medications
- Monitoring and reporting of SAEs

The following will be collected as baseline data on Day -1:

- A serum or urine pregnancy test on women of childbearing potential
- Record of concomitant medications
- Vital signs
- Results from clinical chemistry and hematology laboratory evaluations (refer to [Table 4](#) for specific assessments)
- Monitoring and reporting of AEs including SAEs

The following will be collected as baseline data on Day 1 prior to study treatment administration:

- Blood specimen for anti-PA Ab levels and TNA titers

Additionally, for subjects randomized to Treatment Group 2, the following will be collected as baseline data on Day 1 prior to study treatment administration:

- Blood specimen for anti-raxibacumab Ab level

- Blood specimen for serum raxibacumab concentrations

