9.4.2.3. Safety Analyses

Clinical safety observations will include AEs, urinalysis, vital sign measurements, and clinical laboratory assessments. Safety data will be tabulated and, where appropriate, analyzed by the use of descriptive statistics. Safety data will be tabulated for the Safety Population.

The number (%) of subjects withdrawing from the study will be summarized for each treatment group and the number (%) subjects withdrawing for each individual reason will be summarized by treatment group.

Reported AEs will be coded using MedDRA. The number (%) of subjects in each treatment group with treatment-emergent AEs will be compared for overall incidence and by system organ class and preferred term. Similar summaries will also be presented for deaths, all SAEs, AEs leading to withdrawal, and drug-related AEs. Severity of treatment-emergent AEs will also be summarized by system organ class, preferred term, and treatment group.

Additionally, the frequency of laboratory abnormality events along with shifts from baseline will be summarized, as well as changes over time in laboratory parameters, urinalysis and vital signs.

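### SAP Appendix A leaves out the worsening half of the SAP's own TEAE definition, and SAP 4.12.4.2 makes conditional the death, SAE and withdrawal summaries that the protocol promises outright

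*SAP*

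**What the plan says.** **Treatment emergence.** SAP 4.12.4.2 gives the definition: "A treatment-emergent adverse event (TEAE) is defined as any AE that began or worsened following the start of dosing". Appendix A then gives the algorithm. Where the start date is known, all three stop-date rows (known, partial, missing) carry the rule "If start date < study med start date, then not TEAE". A further start-date category, "Partial, but known components show that it cannot be on or after study med start date", is classed as not TEAE in all three of its stop-date rows. SAP 4.12.4.2 adds "Pretreatment AEs are defined as AEs occurring prior to dosing" and keeps those events to the listings.

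**Summaries of deaths, SAEs and withdrawals.** Protocol 9.4.2.3 first describes counts and percentages of subjects with TEAEs in each treatment group, and continues: "Similar summaries will also be presented for deaths, all SAEs, AEs leading to withdrawal, and drug-related AEs". SAP 4.12.4.2 makes the corresponding listings mandatory but puts a condition on the summaries: "If deemed relevant (depending on the number of such events observed), summaries of SAEs, AEs leading to discontinuation of study drug, and deaths". It gives no threshold and does not say who decides. SAP 4.13, which is meant to record departures from the protocol's analyses, mentions only the handling of ECG intervals.

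**The concern.** Appendix A is titled as a set of partial-date conventions, but its first rows also decide events with complete dates, so a programmer could reasonably take it as the operative rule for every AE. Read that way, it drops half of the definition in the body of the SAP, and nothing says which of the two prevails.

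On the summaries, the SAP turns a firm commitment into a choice made once the number of events is known. SAP 1.0 requires deviations from the SAP to be documented in the study report. Because the SAP itself permits omission, leaving these tables out would not count as a deviation and would not have to be explained.

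Describing the safety of the combination against AVA alone is a stated secondary objective. At stake are the completeness of the TEAE tables and the certainty that the by-arm tables of the most serious events will appear. The primary non-inferiority inference, the futility rules and the data collected are not affected.

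**Working it through.** The plan states no figure that could be reproduced on this point, so the check is a comparison of rules.

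**Step 1. Can such a record exist?** Protocol 7.2 lists "Monitoring and reporting of AEs including SAEs" among the Day -1 baseline activities, and the Time and Events tables for both groups schedule AE assessment on Day -1. The SAP's own category of pretreatment AEs presupposes that pre-dose records may be in the database. The counting rule in SAP 4.12.4.2 that begins "If changes in the DMID grade/severity of an AE are recorded in the eCRF" shows that an upgrade under an existing AE is allowed for, though not that it must be recorded in that way.

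**Step 2. Run Appendix A on an AE that starts before dosing and worsens afterwards.** A stop date known to precede dosing is irrelevant here, because such an AE cannot have worsened after dosing.

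| Start date | Stop date | Appendix A | Definition in 4.12.4.2 |
|---|---|---|---|
| Known, pre-dose | Known, post-dose | Not TEAE | TEAE |
| Known, pre-dose | Partial | Not TEAE | TEAE |
| Known, pre-dose | Missing | Not TEAE | TEAE |
| Partial, must be pre-dose | Known, post-dose | Not TEAE | TEAE |
| Partial, must be pre-dose | Partial | Not TEAE | TEAE |
| Partial, must be pre-dose | Missing | Not TEAE | TEAE |

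The two rules disagree in 2 × 3 = 6 of 6 combinations.

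**Step 3. Find the limits of the conflict.** If the start date is missing, or partial and possibly on or after dosing, Appendix A gives TEAE unless the stop date precedes dosing. If the AE starts on Day 1 but before the dose, the comparison is by date and equality counts, so the result is TEAE. The conflict is therefore confined to AEs whose known start date, or known date components, fall before the study medication start date.

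**Step 4. Size.** Subjects affected per arm = subjects per arm × proportion with an AE ongoing at dosing × proportion of those that worsen within the same record. The documents give neither proportion, so no number can be calculated.

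**Step 5. Compare the summary commitments.**

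| Event | Protocol 9.4.2.3 | SAP 4.12.4.2 |
|---|---|---|
| Deaths | Summary, unconditional | Listing always; summary conditional |
| SAEs | Summary, unconditional | Listing always; summary conditional |
| AEs leading to withdrawal | Summary, unconditional | Listing always, for study withdrawal or permanent treatment discontinuation; the conditional summary names only discontinuation of study drug |
| Drug-related AEs | Summary, unconditional | Table, unconditional |

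The third row changes the event as well as the commitment. Protocol 5.4 lets a subject withdrawn from study treatment remain on the study, so stopping study drug and leaving the study are different events.

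**The case against.** **On treatment emergence,** the protocol goes far towards closing the gap. Section 7.4.1.1 collects AEs from the start of study treatment and says that earlier occurrences may be entered as medical history. The screening schedule captures only SAEs. Appendix 4 treats the exacerbation of a pre-existing condition as an AE in its own right; entered as a new record, it would have a post-dose start date and Appendix A would class it as TEAE. This stands as a reason to expect few cases. It does not remove the conflict: the medical-history route is optional, and nothing requires a new record dated at the worsening.

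**On the summaries,** the condition reads most naturally as a way to avoid near-empty tables. SAEs that are TEAEs still appear in the mandatory tables by system organ class, preferred term and maximum grade. SAP 4.5 tabulates premature discontinuation with its reason by treatment. With few events, a full listing tells a reader almost as much. All of this stands, and it limits the loss to the dedicated by-arm table.

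Some stronger readings are not supported:

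- *Every AE that starts before dosing is excluded.* Step 3 of the working shows otherwise.
- *The algorithm biases the comparison between arms.* It applies to both arms alike, and for missing or ambiguous start dates it leans towards inclusion. Guesses such as 2% of 300 subjects with an ongoing AE, a third of them worsening, give 300 × 0.02 × 1/3 = 2 per arm. Those inputs are not in the documents, and an equal number in each arm shows no distortion.
- *Infusion reactions are lost.* The protocol's risk assessment describes them as arising during administration, so they normally start on Day 1 and count as TEAEs.
- *The affected events vanish from all safety output.* They stay in the AE listings, and laboratory and vital-sign summaries do not depend on TEAE status.
- *The sponsor could drop tables after seeing an unfavourable comparison.* The trigger is the number of events, not their split by arm.
- *SAP 4.13 should have declared both matters.* The protocol does not define treatment emergence, so the TEAE conflict lies within the SAP. Only the change to the summaries is a departure from the protocol.

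**Conclusion.** Both points hold and both are minor.

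The SAP contradicts itself on an AE with a documented pre-dose start that worsens after dosing: the definition counts it, the algorithm does not, and it would be confined to the listings. This assumes that a site keeps the event as one AE record rather than entering the worsening separately, which the documents allow but do not require. The number is probably small in screened healthy volunteers, could arise in either arm, and cannot be calculated from the documents.

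The SAP also weakens, without declaring it, the protocol's commitment to by-group summaries of deaths, SAEs and AEs leading to withdrawal. Since the listings are mandatory, what is lost is the guaranteed count and percentage by arm. This conclusion rests on the wording alone and needs no numerical assumption.

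**What to change.** **Treatment emergence.** Choose one of two routes.

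- Add *unless the DMID grade or seriousness increases on or after the first dose, in which case TEAE* to all six affected rows of Appendix A: the three known-start rows and the three rows for partial dates that must be pre-dose. Amending only the known-start rows would leave three of the six contradictions in place. Add the same exception to the pretreatment-AE sentence in SAP 4.12.4.2. This route needs a date for each grade change, and the documents do not say whether one is collected.
- Or require that worsening after dosing be entered as a new AE dated at the worsening. Appendix A can then stay as it is. The cost is an instruction to sites on completing the eCRF and a check of existing records.

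**Summaries.** Delete the conditional phrase in SAP 4.12.4.2. Always tabulate by arm, including zero counts: deaths, SAEs, AEs leading to withdrawal from the study, and AEs leading to discontinuation of study treatment, with the last two kept as separate rows.

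The cost is a few SAP wording changes, short additional tables, and modest programming if the grade-change route is chosen and the dates are available. No change to the design or sample size is needed.
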